### **9.8. Statistical Termination**

No interim analysis will be conducted as statistical outcomes will not change the conduct of the study.

### **9.9. Statistical Procedure Deviations**

Statistical procedure deviations will be reported to the principal investigator and the sponsor. Deviations from the original statistical plan will be explained in the final study report.

### **9.10. Selection Criteria**

All participants who consent, and are fitted with a mask that they attempt to sleep on will be included in the analysis. Please see section 8.10 for information on participant flow throughout the trial.

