## 6. Justification for a Clinical Trial

### 6.1. Synopsis

The investigation is a prospective, non-randomized, non-blinded, study. The investigation is designed to evaluate the performance, comfort and ease of use of the F&P Toffee Full Face mask amongst OSA participants. Up to 45 OSA participants who currently use a full face CPAP mask will be recruited.

The Institution will recruit all participants within two weeks of the beginning of the study. This study will involve a baseline visit (Visit 1) where the investigator will obtain participants informed consent for the [REDACTED] and the Anthropometric 3D Scanning study [REDACTED]. Participant's demographics and prescribed PAP therapy treatment settings and mask details will be gathered using the participants questionnaire (Appendix B). [REDACTED] device will be issued to the participant during this visit (if required) Visit 2 will take place  $7 \pm 4$  days after Visit 1. At this visit participants will be fitted with the [REDACTED] mask as well as being asked questions in the form of a structured questionnaire. Participants initial impressions, comments and photographs will be captured via recorded audio and video (both with their consent).

Visit 3 will take place 14 ± 4 days after Visit 2. The participants will come in for a final visit to return the trial mask and provide their feedback in the form of verbal comments and a structured questionnaire. Photographs will be captured as well as audio and video recorded during this visit.

The mask and CPAP (if from the research pool) will be returned to the Institution at the conclusion of the trial and the participant will return to their previous mask and mode of device treatment.

This study will be conducted in accordance with ICH/GCP guidelines. No deviation from the protocol will be implanted without prior review and approval of the sponsor except where it may be necessary to eliminate an immediate hazard to a research participant. In such case, the deviation will be reported to the sponsor as soon as possible. In this trial the sponsor and the investigator are the same company however the sponsor will not be the investigator. To ensure roles are clearly defined and kept independent there will be a delegation of authority log to clearly delineate each individuals tasks.

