### 8.4. End Points

#### 8.4.1. Primary Endpoints

- The F&P mask is comfortable to use for the participant as measured by the custom questionnaires and recorded during the interviews.
- The F&P mask is easy to use, accepted by the participant and provides adequate treatment for OSA during in-home use, measured via participant feedback and PAP data download.
- The acceptability of the F&P mask through interview feedback/ questionnaires.

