## 8.5. Variables

Variable	Justification	Measurement
Ease of use/ Acceptability	To assess the ease of using the mask in the home and overall mask acceptability.	
Mask performance	To assess the masks performance in relation to leak	

Mask Comfort	To assess the comfort (or lack of) of the mask as experienced by the participant while using it in-home.
General Demographics	To gather participants general demographics
Preference	To assess which mask the participants prefers to use going forward.
Anthropometric Scans	To assist with future product development

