## **8.11. Withdrawal Criteria**

Participants will be informed that they have the right to withdraw from the study at any time, without prejudice to their medical care, and are not obliged to state their reasons. The participants is informed that they can revert back to their usual therapy during the clinical investigation if they have reason to do so. Additionally the investigator may withdraw a participant at any time for the following reasons:

- Protocol Violation
- Safety concerns
- Serious illness
- Adverse event

The reason for participant discontinuation in the study is to be recorded in the CRF and source document.

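### The single analysis set in 9.10 omits people who could not be fitted or who declined the mask before trying to sleep in it; general acceptability needs a supplementary summary beside it

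*Combined protocol and SAP*

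**What the plan says.** Section 9.10 defines the analysis set: "All participants who consent, and are fitted with a mask that they attempt to sleep on will be included in the analysis". It speaks of the analysis as a whole and gives no separate set for any endpoint. It then adds "Please see section 8.10 for information on participant flow throughout the trial".

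Section 8.4.1 lists three primary endpoints. The second ties ease of use, acceptance and adequate treatment to use at home. The third has no such limit: "The acceptability of the F&P mask through interview feedback/ questionnaires". Section 8.5 describes one variable in these terms: "To assess the ease of using the mask in the home and overall mask acceptability".

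Section 6.1 gives the order of events. Consent is taken at Visit 1. Fitting takes place at Visit 2, 7 ± 4 days later, with participants "as well as being asked questions in the form of a structured questionnaire". At the same visit, "Participants initial impressions, comments and photographs will be captured via recorded audio and video", subject to consent. Sleep at home comes after that.

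Section 8.11 says of withdrawals: "The reason for participant discontinuation in the study is to be recorded in the CRF and source document". It also says that participants "are not obliged to state their reasons".

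**The concern.** Entry to the 9.10 set depends on something close to the outcome. A person whose face the mask does not fit, or who sees it at Visit 2 and will not take it to bed, has told the sponsor something about acceptability. Feedback may even have been recorded that day. Under 9.10 that person is not analysed. Where the reason is the mask, leaving the person out can only move the acceptability result in the mask's favour.

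Two uses of the results are affected. Section 11 allows them to go into marketing or regulatory documents, so a general statement about acceptability may be read outside the development team. Section 9.6 justifies the sample by the share of problems that 30 users would reveal, and a problem that stops the mask from being fitted at all would not be seen among people who were fitted and tried to sleep. This second consequence does not need a planned percentage.

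**Working it through.** **The plan's own figures.** Section 9.6 gives 30 users and recruitment of up to 45. It states no loss rate. The two numbers imply a loss of 1 − 30/45 = 33.3%, which covers drop-outs and no-shows of every kind. It is not a rate of failed fitting or refusal, and I do not use it as one. No acceptance percentage or exclusion rate is visible, so there is no stated acceptability figure to reproduce.

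**Who is in the set**

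| Course after consent | In the 9.10 set? |
|---|---|
| Does not attend Visit 2 | No, but was never offered the mask |
| Cannot be fitted at Visit 2 | No |
| Fitted, declines before any attempt to sleep | No |
| Fitted, does not attempt sleep for an unrelated reason | No |
| Attempts to sleep, then rejects the mask | Yes |
| Completes home use | Yes |

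The point concerns rows two and three. Row four means that not everyone left out has rejected the mask.

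**Size, all exclusions mask-related.** Inputs: N = 45 fitting attempts (the recruitment ceiling in 8.12). Assumed: *e* mask-related exclusions, *a* accepters in the 9.10 set, and acceptance p = a/(N − e) of about 0.8.

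Overstatement = a/(N − e) − a/N = p × e/N.

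| N | e | 9.10 set | All with fitting attempted | Gap (points) |
|---|---|---|---|---|
| 45 | 0 | 36/45 = 80.0% | 36/45 = 80.0% | 0 |
| 45 | 1 | 35/44 = 79.5% | 35/45 = 77.8% | 1.8 |
| 45 | 3 | 34/42 = 81.0% | 34/45 = 75.6% | 5.4 |
| 30 | 1 | 23/29 = 79.3% | 23/30 = 76.7% | 2.6 |
| 30 | 3 | 22/27 = 81.5% | 22/30 = 73.3% | 8.1 |

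**Size, mixed reasons.** Let *u* be exclusions for unrelated or unstated reasons. Take N = 45, e = 1, u = 2.
- 9.10 set: 34/42 = 81.0%.
- Counting the one known mask-related case: 34/43 = 79.1%, a gap of 1.9 points.
- Worst case, both others not accepting: 34/45 = 75.6%.
- Best case, both others accepting: 36/45 = 80.0%.

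**Against sampling uncertainty.** The exact (Clopper-Pearson) 95% interval for 34/42 is 65.9% to 91.4%, which is wide compared with any gap above. The interval does not, however, reflect a bias that runs in one direction.

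**Chance that the issue arises.** If each of 45 people has probability q of a mask-related exclusion, the chance of at least one is 1 − (1 − q)^45: 36% at q = 1%, 60% at 2%, 90% at 5%. All values of q are assumed.

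**The case against.** The strongest reply is that 9.10 already matches what the trial sets out to measure. Section 6.5 asks participants to use the mask so that they can give feedback on comfort and acceptance, just after describing 14 ± 4 days of home use. Sections 2.1 and 7.2 place the purpose in the home, and 8.5 pairs acceptability with ease of use there. This stands, and it supports the 9.10 set as the main one. A reader might infer that 9.10 is simply the wrong population for acceptability; the documents do not support that. What remains is that the third bullet of 8.4.1 and the mention of overall acceptability in 8.5 go wider than home use, and the set does not cover the wider claim.

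The second reply is that the relevant text cannot be seen. In the contents list, 8.10 runs from page 13 to page 18, yet only two sentences of it are shown; 9.7, the measurement column of 8.5 and the questionnaires are also not shown. Any of them may deal with these people. This stands as well, so a reader should not infer that the plan ignores them.

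Third, it is tempting to say that everyone who refuses the mask is dropped, or that problems leading to refusal can never appear in the analysis. Neither is right. One attempt to sleep keeps a person in, and a problem that makes one person decline early may also be reported by others who persist. Only a problem that always prevents fitting is confined to people outside the set.

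Fourth, no acceptance percentage is visible, and 9.5 says that no statistical design is needed. This limits the weight of the arithmetic, but a descriptive statement can be too favourable too.

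**Conclusion.** The point holds as a minor one. On the visible text, a general acceptability statement drawn from the 9.10 set alone is too favourable if anyone is left out for a mask-related reason, and a problem that prevents fitting may go unlisted. The size is unknown. It is zero with no exclusions; for N = 45 and about 80% acceptance it is 1.8 points for one mask-related exclusion and 5.4 for three. Every input except N is assumed, and N = 45 is itself the recruitment ceiling.

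A reader might treat the whole difference between 45 recruited and 30 needed as rejections. At 80% acceptance that would give 24/30 = 80.0% against 24/45 = 53.3%, a gap of 26.7 points. The documents do not support this: the allowance in 9.6 is for drop-outs and no-shows, which include people never offered the mask and people who leave after trying it.

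Confidence is moderate, because the unseen parts of 8.10, 9.7 and the questionnaires could settle the matter.

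**What to change.** Keep the 9.10 set as the main analysis for all endpoints. Add to 9.10 a supplementary acceptability summary over all consented participants in whom fitting was attempted at Visit 2, shown beside the main result, as follows:

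- Report failure to fit and refusal before any sleep attempt on separate lines, so that fit and acceptance are not merged.
- Count as not accepted only those with a recorded mask-related reason.
- Show unrelated and unstated reasons separately in a participant-flow table, with best-case and worst-case counts.
- List the mask problems that these people reported, so that they enter the problem-finding exercise of 9.6.

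If 8.10, 9.7 or the questionnaires already contain such a rule, reconcile 9.10 with it by a reference.

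The cost is two or three sentences and one table, with no extra participants or visits. The summary would use the Visit 2 feedback and the discontinuation reasons that the plan already records. The Visit 2 questionnaire is not shown, so check that it, or the recorded comments, covers people who cannot be fitted. The downsides are a little more tabulation, some people who can be shown only as reason not stated, and a possibly less favourable figure. The rule should be written before the data are analysed, so that the denominator is not chosen with the results in view.

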## **9.11. Statistical Data Management**

Fisher and Paykel Healthcare may consult an external statistician to assist with the analysis of the data.

[figure not shown]
## **10. Adverse Events and Termination**

An Adverse Event (AE) is any adverse change from the participant's baseline condition, i.e., any unfavorable and unintended sign or symptom or disease that occurs during the course of the study, whether or not considered related to the PAP treatment. All clinically significant AEs occurring during the study that were not present prior to the commencement of PAP treatment, will be recorded in the CRF and source document and followed by the Investigator until resolution or stabilization occurs in accordance with GCP.

Serious AE's are considered to be AE's that result in any of the following outcomes, regardless of their relationship to the PAP treatment:

- Death
- A life-threatening AE
- In-patient hospitalization or prolongation of existing hospitalization
- A persistent or significant disability/incapacity
- A congenital abnormality/birth defect

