### 7.3. Population

Up to 45 participants will be recruited for the trial. These participants will be current full face mask users.

Participants will consist of male and female adults diagnosed with OSA who are using either APAP, CPAP or Bi-level with the following recruitment goals:

After identification, the co-ordinating investigator or contact persons from the institution (or those identified by delegation log) will contact potential participants and obtain informed consent from those participants to be enrolled.

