## 8. Clinical Investigation Design

### 8.1. Type of Investigation

This is an open-label (investigators and participants are un-blinded and informed of intended treatment device) single arm study. The F&P Toffee full face mask will provide effective treatment similar to the participant's usual CPAP mask. The intended treatment F&P Toffee full face mask will not be randomized- as the intention is not to compare between therapies.

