## 8.6. Measurements

## **8.8. Inclusion / Exclusion criteria**

Inclusion Criteria:

- Adult (22+ years of age)
- Able to give informed consent
- AHI  $\geq 5$  on diagnostic night
- Either prescribed APAP, CPAP or Bi-level PAP for OSA
- Fluent in spoken and written English
- Existing Full Face mask user

Exclusion Criteria:

[figure not shown]
- Inability to give informed consent
- Participant intolerant to PAP
- Anatomical or physiological conditions making PAP therapy inappropriate
- Current diagnosis of respiratory disease or CO2 retention
- Pregnant or may think they are pregnant.

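### Section 10 defines adverse events against baseline but records them against an undefined start of PAP treatment, in participants who are already on PAP

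*Combined protocol and SAP*

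**What the plan says.** Two consecutive sentences in section 10 of the combined protocol and SAP matter here. The definition reads: "An Adverse Event (AE) is any adverse change from the participant's baseline condition". The recording rule reads: "All clinically significant AEs occurring during the study that were not present prior to the commencement of PAP treatment, will be recorded". The first looks back to baseline, the second to the start of PAP treatment.

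Section 6.1 (Synopsis) calls Visit 1 the baseline visit and has the trial mask fitted at Visit 2, 7 ± 4 days later. It also describes the population: "Up to 45 OSA participants who currently use a full face CPAP mask will be recruited". Section 7.3 repeats this ("These participants will be current full face mask users"), and section 8.8 makes it an inclusion criterion ("Existing Full Face mask user") alongside a PAP prescription for OSA. Section 6.5 keeps participants on their prescribed pressure.

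The visible text does not define the start of PAP treatment, and it uses the word treatment in two senses. At Visit 1, "prescribed PAP therapy treatment settings and mask details will be gathered", which refers to the therapy the participant already has. Section 8.1 uses it of the trial mask: "The intended treatment F&P Toffee full face mask will not be randomized".

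Section 10.3 requires every serious event in the study period, whatever its cause, to be reported and entered on the AE page of the CRF.

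**The concern.** A recording rule should pick up the events that the definition creates. Here the rule adds a condition tied to a different and undefined date. The wording would suit a study in which PAP is started. In this one, PAP is already under way and only the mask changes.

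What is at stake is complete and consistent recording of non-serious harm. Section 8.2 provides no control group, so change from the participant's own earlier state is the natural basis for judging such harm. Section 6.2 links poor mask fit in general to facial abrasion and eye irritation, so some existing users could enter with these problems. Section 10.2 lists similar problems as foreseeable with the trial mask. Section 11 allows the results to be used in marketing or regulatory documents, so the safety record may be read outside the development team.

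**Working it through.** The plan gives no figure on this point, and the only arithmetic is the interval between visits. The check is to apply the definition and the recording rule to the same kinds of non-serious, clinically significant event under each meaning of the undefined term.

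**Inputs.** Definition and recording rule: section 10. Baseline = Visit 1, and trial mask fitted at Visit 2: section 6.1. Interval between them: 7 − 4 = 3 days to 7 + 4 = 11 days. All participants already on PAP with a full face mask: sections 6.1, 7.3 and 8.8.

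**Where the reference point falls.**
- Reading A, prescribed PAP: before Visit 1 for every eligible participant.
- Reading B, the trial mask: at Visit 2, so 3 to 11 days after baseline.

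**What the rule then does.** In this table, *present* is taken to refer to the underlying condition.

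| Event during the study | AE by the definition? | Recorded under A? | Recorded under B? |
|---|---|---|---|
| Condition older than PAP that recurs or worsens | Yes | Can be left out | Can be left out |
| Skin or eye problem from the usual mask that worsens on the trial mask | Yes | Yes, because it arose after PAP began | Can be left out |
| Usual-mask problem, unchanged | No | Not applicable | Not applicable |
| New problem first arising between Visit 1 and Visit 2 | Yes | Yes | Can be left out |
| New problem first arising after Visit 2 | Yes | Yes | Yes |

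**Reading C, each worsening is itself the event.** A worsening during the study was not present earlier, so rows 1 and 2 are recorded under A. They are also recorded under B if the worsening comes after Visit 2. What remains is anything that first arises or worsens between Visit 1 and Visit 2 under B.

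**Serious events.** Section 10.3 captures them under every reading, so all the possible gaps concern non-serious events.

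The two readings lose different things. Under A the reference point lies before the study for everyone, but worsening of usual-mask problems is still recorded. Under B that worsening can be lost, but the reference point lies inside the study.

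**The case against.** The strongest reply is that the two sentences do not contradict each other. The first says what an adverse event is, and the second is a narrower filter on which of those events are recorded. The filter speaks of events rather than underlying conditions, so if the event is the change, a worsening during the study was not there before and is recorded. Section 10 also mentions PAP treatment when it discusses relatedness, which suggests treatment within the study and hence the trial mask. Questionnaires, comments and photographs at Visits 2 and 3 also capture mask problems, although they are not adverse event records. Finally, parts of the protocol and the CRF are not visible, and a definition may stand there.

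Much of this stands. The sentences are not in head-on conflict, reading C loses little, and the trial mask may well be the intended meaning. But the text does not choose among the readings. The trial-mask reading also brings its own gap, because it moves the reference point to Visit 2 while the definition stays at baseline.

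A reader might infer something stronger: that because all participants were on PAP beforehand, worsening of usual-mask skin and eye problems goes unrecorded in all of them. The documents do not support this. It joins the reference point of reading A to the loss of reading B, and no single reading gives both.

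**Conclusion.** The point holds as a minor matter of safety-data recording. The recording rule rests on an undefined date that does not fit a population already on PAP. Depending on the meaning given to it, different kinds of non-serious event can go unrecorded. Under prescribed PAP these are recurrence or worsening of conditions older than PAP. Under the trial mask they are chiefly worsening of usual-mask skin or eye problems and events first arising in the 3 to 11 days between Visit 1 and Visit 2.

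The size cannot be given in events, because the documents state no frequency for such problems and none is assumed here. It would be wrong to infer that serious events are missed, since section 10.3 covers them, or that a result is biased. Adverse events are not among the visible endpoints, section 9.5 declares no statistical design, and neither the sample size nor any estimate depends on this clause.

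The conclusion rests on two assumptions: that baseline in section 10 means Visit 1, as the wording of section 6.1 implies, and that no hidden part of the protocol or CRF defines the start of PAP treatment.

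**What to change.** In the recording sentence of section 10, replace the condition about PAP treatment with *new, or worsened in severity or frequency, since the baseline visit (Visit 1)*. The rule then uses the same reference point as the definition and states that worsening counts, which settles all three readings. Visit 1 is proposed because it is the only visit that the document calls baseline. If the sponsor prefers another visit, the definition should be changed with it so that both sentences share one date.

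The cost is one phrase and slightly more adverse event recording, including some events that arise before the trial mask is fitted. Design and sample size are unchanged.

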### 5.2. Device Risk Analysis and Management

Positive airway pressure (PAP) therapy via a nasal or oro-nasal mask is standard clinical practice for participants with OSA. The risks associated with this treatment are limited to the potential for slight discomfort associated with the use of a oro-nasal mask during sleep.

[REDACTED]

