## **10.2. Foreseeable Adverse Events**

The participants may experience a poor night's sleep with the F&P Toffee full face mask as it will be different to the participants usual mask.

Participants may experience the following:

- Pressure sores which may resolve in cuts, rashes and skin abrasions and skin breakdown
- Air leaks into the eye which may cause discomfort, dryness and irritation
- Abrasions to the skin from the headgear
- Eyelid injury and scratches while removing the mask
- Allergies to the mask material
- Collapsing or passing out possibly due to lack of oxygen which can lead to suffocation in some circumstances
- Pressure discomfort in, around, on the sides and under the nose as their usual mask seal and frame may be configured differently

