## **10.3. Reporting Adverse Events**

Any serious AE, due to any cause, that occurs during the study period, must be reported immediately (within the next business day) by telephone to the sponsor. In addition to the initial telephone report, a Serious Adverse Event form must be completed and sent via facsimile to the sponsor. All serious AE's must also be recorded on the AE page of the CRF. Additionally, all serious AE's must be reported to the Independent Review Board (IRB) as per the IRB's requirements.

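### Section 10 requires recording only of clinically significant adverse events, an undefined term, so non-serious skin, eye and pressure effects that section 10.2 foresees can be left out of the AE record

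*Combined protocol and SAP*

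**What the plan says.** Section 10 opens with a broad definition: "An Adverse Event (AE) is any adverse change from the participant's baseline condition". It goes on to include "any unfavorable and unintended sign or symptom or disease that occurs during the course of the study", whether or not the event is thought related to PAP treatment. No threshold of severity or significance is attached.

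The next sentence sets the recording rule: "All clinically significant AEs occurring during the study that were not present prior to the commencement of PAP treatment, will be recorded". It applies to the CRF and the source document, and it also requires the investigator to follow the recorded events until they resolve or stabilise.

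Section 10.2 lists effects that the protocol expects as AEs. They include "Abrasions to the skin from the headgear", "Air leaks into the eye which may cause discomfort, dryness and irritation" and "Pressure discomfort in, around, on the sides and under the nose". The same list contains graver events, such as skin breakdown, eyelid injury and collapse. Section 5.2 describes the risks of treatment as "limited to the potential for slight discomfort associated with the use of a oro-nasal mask during sleep".

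Two other rules put events on file whatever their significance. Section 10.3 covers serious events: "All serious AE's must also be recorded on the AE page of the CRF". Section 8.11 requires the reason for any discontinuation to be recorded.

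**The concern.** The protocol expects mainly minor harms from the mask, and its recording rule lets minor harms go unrecorded. With clinical significance undefined in the readable text, two members of staff applying the rule in good faith could record the same abrasion differently. The study has one arm (section 8.1) and no control group (section 8.2), so incomplete recording would not show up in a comparison.

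What is at stake is the completeness of the AE record and of anything written from it. Section 11 says that the study is meant for internal product development, but allows the results to be used in marketing or regulatory documentation. A short AE list could then be read as a property of the mask when it is partly a product of the recording rule.

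The rule's second condition does not fit the definition either. It excludes events present before PAP treatment began, whereas the definition measures change from the participant's baseline. Every participant is already a full face mask user on prescribed PAP at entry (section 8.8), so the two reference points differ.

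**Working it through.** The documents give no AE rate, safety threshold or safety analysis, so there is no stated figure to reproduce. The check is mainly a comparison of text.

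**Step 1: definition against recording rule.**

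| Type of event | AE under section 10? | Recording required? |
|---|---|---|
| Serious | Yes | Yes (10.3) |
| Leads to discontinuation | Yes | Reason recorded (8.11) |
| Non-serious, judged clinically significant, new since PAP began | Yes | Yes (10) |
| Non-serious, judged not clinically significant, participant continues | Yes | No rule in the readable text |

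The last row is the gap. A non-serious abrasion, eye irritation or pressure discomfort of a type listed in 10.2 can fall into it.

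**Step 2: the onset condition.** Read literally, a mark caused by the participant's usual mask arose after PAP began, so it passes the condition even if nothing has changed since baseline. If the start of PAP is instead read as the start of the trial mask, a sore already present that worsens on the trial mask was there beforehand and is excluded, although it is an adverse change from baseline. Neither reading matches the definition.

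**Step 3: scale, for illustration only.** Inputs from the documents are n = 30 (target users, section 9.6) and n = 45 (maximum recruited, section 8.12). Assumed inputs are p, the share of users with a mild mask effect, and q, the share of those effects judged clinically significant. Each affected user counts once.

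- Expected users affected = n × p.
- Expected users recorded = n × p × q.
- Chance that none is recorded = (1 − p × q)^n.

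| n | p | q | Affected | Recorded | Chance of none recorded |
|---|---|---|---|---|---|
| 30 | 20% | 100% | 6.0 | 6.0 | 0.80^30 = 0.1% |
| 30 | 20% | 50% | 6.0 | 3.0 | 0.90^30 = 4.2% |
| 30 | 20% | 25% | 6.0 | 1.5 | 0.95^30 = 21.5% |
| 45 | 20% | 100% | 9.0 | 9.0 | 0.80^45 < 0.1% |
| 45 | 20% | 50% | 9.0 | 4.5 | 0.90^45 = 0.9% |
| 45 | 20% | 25% | 9.0 | 2.25 | 0.95^45 = 9.9% |

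Over p from 10% to 40% and q from 10% to 50%, the chance of recording none runs from 0.1% to 74% at n = 30 and from under 0.1% to 64% at n = 45.

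As a reported proportion, 6/30 = 20% has an exact (Clopper-Pearson) 95% interval of 7.7% to 38.6%, and 3/30 = 10% has 2.1% to 26.5%. The intervals overlap widely. They describe sampling error only and give no warning that events were filtered out.

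**The case against.** The strongest reply is that nothing the plan intends to report is harmed. The primary endpoints concern comfort, ease of use, acceptability and adequate treatment (section 8.4.1), section 9.5 disclaims any statistical design, and no AE rate or AE table is specified. Section 11 mentions support for efficacy, not for safety. This stands: a reader might infer that a planned safety result is invalid, and the documents do not support that. The point concerns the AE record and any report that draws on it.

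A broad definition with a narrower recording threshold is also not a contradiction. That stands too; it is a choice, and its effect is a less complete record.

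A reader might infer that AE counts will be biased low. The documents support only that they can be. An investigator who records generously could lose nothing, and both p and q above are assumptions. Section 10.2 does not grade its events, so calling the skin, eye and pressure effects mild is an inference, supported in part by section 5.2.

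A reader might also infer that staff with an interest in the product will decide what counts. Section 10 does not say who judges significance. Section 6.1 says that sponsor and investigator belong to the same company, but also that the sponsor will not be the investigator and that a delegation log keeps the roles independent. The documents do not support a charge of selective recording.

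Finally, questionnaires and interviews measure comfort and may pick up some of these effects. The questionnaire content, much of the procedure section and the CRF section cannot be read in the public text, and their absence is not a fault of the plan. The possibility stands but cannot be checked, and no readable text carries such answers into the AE record.

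**Conclusion.** The point holds in a limited form. The stated rule allows non-serious events that meet the protocol's own definition, including types listed in 10.2, to go unrecorded, and the term that decides this is undefined in the readable text. The fall from 6/30 to 3/30 shows only what a 50% filter would do to an assumed 20% rate; the actual loss is unknown and could be nil. The conclusion rests on the unreadable sections not containing a definition of clinical significance or a separate route into the AE record. This is a cheap improvement to data capture, worth making because the results may be used outside the company. It does not undermine the study's stated endpoints.

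**What to change.** In section 10, separate recording from follow-up.

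- **Recording:** require every AE that meets the section 10 definition to be recorded over the whole course of the study, starting at Visit 1, and state that this includes every event of a type listed in 10.2. Starting at the Visit 2 mask fitting would lose events in the 7 ± 4 days after Visit 1, when a device may already have been issued (section 6.1).
- **Fields for each event:** severity, relatedness to the mask, clinical significance, and whether onset or worsening came before or after the Visit 2 mask fitting. Clinical significance then describes the event and no longer decides whether it is recorded.
- **Follow-up:** leave the existing follow-up clause applying to clinically significant AEs as now written. Simply deleting the qualifier would extend that duty to every minor event.
- **Reference point:** reconcile the condition about the start of PAP treatment with the baseline in the definition, since all participants already use PAP at entry.

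The cost is a revised rule and a few more CRF lines for at most 45 people, each in the study for 13 to 29 days by the visit windows (3 + 10 to 11 + 18). The downside is a longer and less favourable-looking list of minor AEs, which the severity and relatedness fields would put in context.
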